- d. Sitting Blood Pressure and Pulse Rate: Sitting, triplicate blood pressure and pulse rate measurement to be collected as per [Section 7.7](#).
- e. Duplicate measurements of supine and standing blood pressure and pulse rate as per [Section 7.8](#).
- f. ECG is reviewed at the investigative site for safety monitoring and submitted for central reading as per [Section 7.5](#). If a subject experiences a non-fatal myocardial infarction after randomization, a new baseline ECG should be performed between 6 and 12 weeks following the myocardial infarction, at an unscheduled visit if necessary.
- g. Routinely collected urinalysis samples will be sent to the central laboratory for dipstick analysis and microscopy if dipstick is positive for blood, nitrites, leukocytes and/or protein. Urinalysis should not be collected for a female subject who is menstruating.
- h. Urine pregnancy tests will be performed for women of childbearing potential at all time points and if positive may be confirmed with a serum pregnancy test. Pregnancy tests may also be repeated at any time if requested of IRB/IECs or if required by local regulations as per [Section 7.1.6](#).
- i. Site fingerstick HbA1c is not mandatory, but may be used at the discretion of the investigator for screening subjects. However, a fingerstick HbA1c cannot substitute for a central laboratory-measured HbA1c to determine if a subject meets entry criteria.
- j. Includes total cholesterol, HDL-C, LDL-C, non-HDL-C and triglycerides at all time points. If LDL-C is measured directly on a Day 1 sample, the central laboratory will perform direct LDL-C measurements on subsequent samples for that subject.
- k. Samples should not be obtained if the subject is menstruating, has vigorously exercised within 24 hours or had fever or an active infection within 2 days of the visit.
- l. The Future Biomedical Research (FBR) informed consent must be obtained before FBR samples are drawn. The FBR sample for DNA analysis should be obtained pre-dose, at the Day 1 visit (V2) as the last sample drawn, on subjects who qualify for randomization, but may be obtained at a later date during the trial after the FBR informed consent is obtained. The plasma and serum samples for FBR should be collected at Day 1 (pre-dose), Week 18, Week 52 or Early Termination Visit, End of Study Visit and Glycemic Rescue Visit (if applicable). The plasma and serum samples for FBR should be collected at all time points, even if the pre-dose or other time point was not collected.
- m. Assess AEs, SAEs and potential clinical events for adjudication as per [Section 8.4.1](#) and [Section 7.1](#).
- n. Subjects will be instructed to contact the site if they are admitted to the hospital for any reason, or if they experience a cardiovascular event.

090177e187d04317\Approved\Approved On: 14-Mar-2016 14:12

- o. If the trial is deemed not complete by Visit 20 (Month 60), visits will continue on an every 4 month schedule and the list of procedures to be performed are the same as the visits for Months 52, 56 and 60 respectively until trial completion (EOS). Unscheduled visits are allowed at any time as needed for assessment of adverse events, repeat laboratory testing, etc.
- p. ET = Early termination, subjects who discontinue taking investigational product prematurely but remain in the study should complete procedures for the ET visit and have a 2 week (14 days \pm 3 days) follow-up phone call from their last dose of investigational product. They will also be contacted via telephone by the investigator/designated representative according to the same schedule as if the subject were still taking investigational product through the end of the trial (ie, according to the [Schedule of Activities](#) and [Section 6](#), study assessments). Subjects will be expected to attend annual visits in person. See [Section 6.3.3](#) for additional details.
- q. EOS = end of study. All EOS procedures should be performed for all randomized subjects when the trial is completed. EOS procedures should be completed whether or not the subject is taking investigational product when the trial is terminated.
- r. Hypoglycemia Assessment and Blood Glucose Self-Monitoring logs will not be dispensed at ET or EOS visits.

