For subjects enrolled under the original protocol, at the time of randomization, subjects will be stratified into the main cardiovascular study, the insulin (with or with metformin) sub-study or the SU monotherapy sub-study, according to their background anti-hyperglycemic treatment as follows. Subjects receiving background insulin (with or without metformin) at doses specified in the protocol are included into the insulin (with or without metformin) add-on glycemic sub study; subjects receiving background SU monotherapy (at doses specified in the protocol) are included into the SU monotherapy add-on glycemic sub-study. Subjects receiving background metformin with SU at doses specified in the protocol are included in the metformin plus SU sub-study. Unlike the other two sub-studies, inclusion in the metformin with SU sub-study will not be determined at the time of randomization. Instead, all subjects randomized into the main cardiovascular study who meet the additional eligibility requirements will be considered enrolled in this sub-study. Since all the subjects participating in the three sub-studies are enrolled in the main cardiovascular study, visit schedules and protocol-required tests and procedures are the same for all subjects irrespective of whether or not a subject also participates in a sub study. The glycemic sub-studies will run during the initial 18 weeks of the study. Following the collection of efficacy and safety end points at Week 18 (V5), subjects in the glycemic sub-studies will continue participating in the main cardiovascular study.

Study Treatments:

Subjects will be randomized in a 1:1:1 ratio to receive ertugliflozin 5 mg, ertugliflozin, 15 mg ertugliflozin or matching placebo once daily added to their background therapy.

090177e187d04317\Approved\Approved On: 14-Mar-2016 14:12

Statistical Methods:

Sample Size

The cardiovascular safety of ertugliflozin will be assessed in two stages. Stage 1 will consist of a meta-analysis of MACE plus events across the Phase 2 and Phase 3 development program with the majority of events expected to come from this trial. Stage 2 will consist of an analysis of MACE and secondary endpoints [eg, Cardiovascular (CV) death or hospitalization for heart failure (composite), CV death (individual component), and renal composite] in this trial. The two doses of ertugliflozin (5 and 15 mg) will be pooled for the purpose of all these analyses.

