Stage 2 of the trial uses a group sequential design with up to two analyses: an interim analysis and a final analysis. The Stage 2 interim analysis and the final analysis are planned to occur when approximately 714 and 939 adjudicated MACE events have accrued in this study. These analyses will assess the hazard ratio for the MACE endpoint with respect to the 1.3 non-inferiority margin. If non-inferiority is established for the primary MACE endpoint, then tests of superiority on the secondary endpoints of CV death or hospitalization for heart

failure (composite), CV death (individual component), and the renal composite will also be performed in a sequential manner. If any of the first three tests in this four step testing sequence are unsuccessful at the interim analysis, the study may be continued to the final analysis (depending on the result of futility assessment).

For the primary Stage 2 analyses, using an O'Brien-Fleming type alpha spending function and analyses at approximately 714 and 939 adjudicated MACE events, the study will have approximately 96% power to demonstrate non-inferiority of ertugliflozin to placebo when there is truly no difference between treatments (HR=1.0) using the non-inferiority margin of 1.3 and testing at the overall one-sided alpha level of 0.025.

With two enrollment periods of 19 months each and assuming an event rate of 3.5% per annum for MACE, a total of approximately 8000 subjects (about 4000 per enrollment cohort) randomized in a 1:1:1 ratio to ertugliflozin 5 mg, ertugliflozin 15 mg or placebo will be sufficient to accrue approximately 714 MACE events within approximately 5.0 years and approximately 939 MACE events within approximately 6.1 years from the start of this study. These calculations assume that subjects will withdraw from the study at a rate of 5% per annum.

Power for Secondary Hypotheses

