For the Stage 2 analyses of secondary endpoints, using an O'Brien-Fleming alpha spending approach and assuming accrual of at least 442 and 582 composite events of cardiovascular death or hospitalization for heart failure at the interim and final analysis respectively, the study will have approximately 90% power to demonstrate superiority of ertugliflozin to placebo on the composite endpoint of cardiovascular death or hospitalization for heart failure when the true HR=0.75. Moreover, assuming accrual of at least 287 and 377 cardiovascular death events at the interim and final analysis respectively, the study will have approximately 83% power to demonstrate superiority of ertugliflozin to placebo on cardiovascular death when the true HR=0.725. With accrual of at least 144 and 190 renal composite events at the interim and final analysis respectively, the study will have approximately 79% power to demonstrate superiority of ertugliflozin to placebo on the renal composite endpoint when the true HR=0.65.

Cardiovascular Endpoints Analysis:

The two doses of ertugliflozin will be pooled for the analysis of all cardiovascular endpoints. The analyses described below will be performed at each interim analysis and at the end of the trial.

The Stage 1 meta-analysis population will include all randomized subjects who have taken at least one dose of investigational product across the Phase 2 and 3 development program. The Stage 2 non-inferiority analysis population will include all randomized subjects who have taken at least one dose of investigational product in this study. For both stages, subjects will be analyzed in the group to which they were assigned by the Interactive Voice Response System (IVRS), regardless of the actual treatment received, and only events confirmed by the Endpoint Adjudication Committee will be included in the analysis. For Stage 1, all

confirmed MACE plus events will be included in the primary analysis. For Stage 2, confirmed MACE events occurring between randomization and 365 days after the last dose of study treatment will be included in the primary non-inferiority analysis.

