Once the 1.8 threshold has been met, the study will continue to Stage 2. An interim analysis will take place when approximately 714 MACE events have accrued in this study. The purpose of this analysis will be to rule out an HR of 1.3 for MACE and to sequentially test for superiority on the secondary endpoints of cardiovascular death or hospitalization for heart failure (composite), cardiovascular death (individual component), and the renal composite. If necessary (ie, if the interim analysis fails to rule out an HR >1.3 or to achieve superiority on both of the secondary CV endpoints), the final analysis will take place after accrual of approximately 939 MACE events. For the primary non-inferiority analysis of MACE, the two-sided adjusted CI for the HR will be calculated using an O'Brien-Fleming spending function to preserve the overall Type I error rate of 2.5% with respect to the non-inferiority margin of 1.3. The analysis at approximately 714 MACE events corresponds to an information fraction of approximately 76%, and the amount of alpha to be spent for this analysis is about 1.0% (one-sided). The subsequent secondary hypothesis tests will utilize a similar O'Brien-Fleming alpha spending approach with a 2.0% two-sided alpha spend for each hypothesis at the interim. If at the end of the study, the upper bound of the two-sided adjusted CI is <1.3 for MACE, the study will be considered to have met its primary objective of demonstrating the non-inferiority of ertugliflozin as compared to placebo with respect to cardiovascular safety. Details regarding alpha spending and power for the primary analyses at each potential analysis time are described in Table 6 below.

Table 6. Alpha Adjusted Confidence Interval and Power for Primary Analyses

Stage	Analysis (within Stage)	Events (confirmed by adjudication)	Alpha for adjusted confidence interval (one-sided)	Power to Demonstrate Non-Inferiority*
1 Phase 2 and 3 Meta-analysis	1 Interim	130 MACE plus	1.0%	79.5%
	If the upper bound at interim analysis is ≥ 1.8 for MACE plus			
	2 Final	173 MACE plus	2.2%	95.1% (cumulative)
Once the 1.8 threshold has been met, the study will continue to Stage 2				
2 Study P004/B1521021	1 Interim	714 MACE	1.0%	83.8%
	If the upper bound at interim analysis is ≥ 1.3 for MACE			
	2 Final	939 MACE	2.2%	96.4% (cumulative)

* Power under HR=1.0

090177e187d04317\Approved\Approved On: 14-Mar-2016 14:12

Interim Futility Analysis for Secondary Endpoints

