Primary test successful and CV death/hospitalization for heart failure composite endpoint unsuccessful but not futile	Study continues to final analysis
Primary test successful and CV death/ hospitalization for heart failure composite endpoint futile	Study may be stopped for success on the primary objective and futility on the secondary superiority objectives
Primary test and CV death/ hospitalization for heart failure composite both successful; CV death unsuccessful	Study continues to final analysis
Primary test, CV death/ hospitalization for heart failure composite, and CV death all successful	Study may be stopped for success (regardless of the outcome for the renal composite)

The interim analyses will be performed by an independent team of statistician(s) and programmer(s) and will be reviewed by the E-DMC to determine whether excess risk with ertugliflozin relative to the non-ertugliflozin comparator group or to placebo (HR>1.8 or 1.3) may be ruled out. The results of the meta-analysis (Stage 1) will be submitted to regulatory authorities. Only upon request from or with agreement of regulatory authorities may the three glyceamic sub-studies be analyzed and submitted while the main study is on-going.

9.8. Insulin with or without Metformin, SU Monotherapy Add-on and Metformin with SU Glycemic Sub-Study Analyses

Primary Efficacy Analyses: The primary analysis population for each sub-study will be the sub-study Full Analysis Set defined as all subjects randomized receiving those specific background treatments at baseline, who meet all sub-study inclusion criteria (eg, minimal

090177e187d04317Approved\Approved On: 14-Mar-2016 14:12

dose(s) and dose stable period), who have received at least one dose of investigational product and have at least one observation of HbA1c during the time of the sub-study, including baseline and post-baseline time points up to Week 18 inclusive. If subjects receive glycemic rescue therapy, the observations post rescue therapy will be excluded from efficacy analyses of the primary and secondary endpoints.

The primary endpoint of HbA1c will be analyzed using a constrained longitudinal data analysis (cLDA) model with the following fixed effects:

- Treatment (categorical);
- Visit (categorical);
- Treatment by visit interaction;
- Baseline eGFR;
- Metformin use (yes/no; applicable for insulin (with or without metformin) sub-study only).

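### If the trial stops at the Stage 2 interim after tests 1–3 succeed, the protocol provides one renal test only (2% two-sided, about 144 events, 54% power) and sets no level for the close-out data

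*Protocol*

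**What the plan says.** Renal superiority is a formal secondary hypothesis (Protocol 2.1.2) and step 4 of the confirmatory sequence (9.3). It is planned with two looks: "With accrual of at least 144 and 190 renal composite events at the interim and final analysis respectively". For that pair of looks, the section on power for the secondary hypotheses claims that "the study will have approximately 79% power to demonstrate superiority of ertugliflozin to placebo on the renal composite endpoint when the true HR=0.65". The alpha chart in 9.7 gives it 2% two-sided at the interim and 4.4% at the final analysis.

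Whether that final analysis happens depends on tests 1–3 only. The Protocol Summary says "If any of the first three tests in this four step testing sequence are unsuccessful at the interim analysis, the study may be continued", and 9.1 repeats this. Section 9.7 schedules the final analysis at about 939 MACE events, if necessary, and explains the condition as "if the interim analysis fails to rule out an HR >1.3 or to achieve superiority on both of the secondary CV endpoints". A failed renal test does not trigger it. When tests 1–3 all succeed, the last row of the action table reads "Study may be stopped for success (regardless of the outcome for the renal composite").

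Section 6.3.3 and the Schedule of Activities require an End of Study visit, with chemistry, for all randomized subjects once the trial closes.

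**The concern.** In the branch where the drug does best on the cardiovascular endpoints, the gate to the renal hypothesis is open, but the text supplies only the first of its two looks. Subjects still attend close-out visits, serum creatinine is still measured, and late doublings and renal events are still recorded. The protocol gives no level at which those data may be tested.

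Section 9.7 does say what happens at the final analysis to MACE and to CV death/heart failure hospitalization if they succeed early and the study continues. It has no matching rule for a renal test that has not succeeded when the study stops. A true renal benefit could therefore miss a confirmatory claim for want of a sentence in the plan. A rule written after the interim would look data-driven.

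**Working it through.** **Inputs from the protocol.** Allocation is "randomized in a 1:1:1 ratio to ertugliflozin 5 mg, ertugliflozin 15 mg or placebo", and "The two doses of ertugliflozin (5 and 15 mg) will be pooled for the purpose of all these analyses", so the comparison is 2:1 and information is (1/3)(2/3) = 2/9 per event. Renal events are 144 and 190, with HR 0.65. The interim level is set by "with a 2.0% two-sided alpha spend for each hypothesis at the interim" (z = 2.326). The final level is 4.4% two-sided (z = 2.014).

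**Formula.** Drift at D events: δ(D) = √(2D/9) × |ln 0.65| = √(2D/9) × 0.4308. Looks at D1 and D2 events have correlation √(D1/D2).

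**Reproducing the plan.**
- δ(144) = 2.437, δ(190) = 2.799, correlation √(144/190) = 0.871.
- Two-look power = 1 − Φ₂(2.326 − 2.437, 2.014 − 2.799; 0.871) = 79.2%, against 79% stated.
- The same method gives 90.0% for CV death/heart failure hospitalization and 83.1% for CV death (stated 90% and 83%).
- One-sided error of the 1.0% and 2.2% pair at 144 and 190 events is 2.50%.

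**Interim look alone.** Φ(2.437 − 2.326) = Φ(0.111) = 54.4%.

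**How often the branch could arise.** At the planning HRs and MACE HR 1.0, interim success probabilities are 83.8% for MACE (Table 6), 70% for CV death/heart failure hospitalization (9.1) and, by the formula above with 287 events and HR 0.725, 59.6% for CV death. The joint probability cannot exceed 59.6%. Under independence it is 0.838 × 0.70 × 0.596 = 35%. CV death is a component of both other endpoints, so positive dependence is expected and the plausible range is about 35% to 60%.

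**Close-out events (assumed).** The documents give no close-out lag. Between years 5.0 and 6.1 the plan expects 190 − 144 = 46 renal events, or 46/13.2 ≈ 3.5 a month. A lag of 1, 3 or 6 months gives about 148, 155 or 165 events.

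**Two possible rules for a last renal test at close-out.**
- (a) O'Brien-Fleming-type spending for the actual events against 190: cumulative one-sided α(t) = 2[1 − Φ(2.241/√t)], with t = D/190. The level is solved so that the two looks together spend α(t).
- (b) 4.4% two-sided.

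| Events | t | (a) cumulative spend, one-sided | (a) level, two-sided | (a) power | (b) power | (b) one-sided error, stop independent of renal | (b) worst-case one-sided error |
|---|---|---|---|---|---|---|---|
| 148 | 0.779 | 1.11% | 1.7% | 57% | 68% | 2.21% | 2.9% |
| 155 | 0.816 | 1.31% | 2.1% | 61% | 70% | 2.26% | 2.8% |
| 165 | 0.868 | 1.62% | 2.7% | 67% | 73% | 2.34% | 2.7% |

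The worst case lets whoever decides on stopping see the interim renal statistic and choose whichever of close-out or 190 events gives the larger chance of a false renal claim. Under (a) the same calculation stays at 2.50%. Under (b), when stopping was driven by a CV statistic correlated with the renal one, simulated error stayed at or below about 2.5% for correlations up to 0.8.

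**The case against.** The strongest reply is that this is a deliberate priority. The sponsor ranked renal fourth and says openly that it will not prolong the trial for it. Any group-sequential trial that stops early leaves lower-ranked hypotheses with unspent alpha. No stated figure is wrong, since 79% is the two-look power and it reproduces. All of this stands. It answers a demand to keep the trial running for renal; it does not answer the question of how data that will be collected anyway should be tested.

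A reader might infer that the renal 4.4% is forfeited. The documents do not support that. Stopping is permitted, not required. The alpha chart attaches no condition that removes the level. The Protocol Summary and 9.2 mention analyses at the end of the trial, although neither sets a renal level for an end before 939 MACE events. The SAP supplied is a heart-failure supplement, so the primary SAP, which may deal with this, could not be checked. What can be said is that the protocol is silent.

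A reader might also infer that a 4.4% close-out test costs nothing and always preserves the error rate. That is too strong. Stopping is discretionary and the data monitoring committee reviews the interim analyses, so dependence of the stopping decision on the renal result is not excluded, and error could then exceed 2.5%. Nor is 4.4% interchangeable with the spending-function level, which yields clearly less power.

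**Conclusion.** The point holds as a gap in the plan; there is no arithmetic error and no inflation of error in what is written. If tests 1–3 succeed at the interim and the sponsor stops, only a 54%-power renal look is provided for. A pre-specified close-out test would raise this by about 2 to 13 percentage points under rule (a) or 13 to 19 under rule (b). It would leave the sponsor's stopping priority unchanged.

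These sizes rest on HR 0.65, on 144 interim events and on an assumed lag of 1 to 6 months. The 144 is itself a planning figure: interim power is 46% at 120 events and 60% at 160. The frequency of the branch assumes that all the planning effects are true.

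**What to change.** In Protocol 9.7 (last row of the action table and the renal row of the alpha chart), mirrored in 9.1 and the Summary, add the following. If the study is stopped after tests 1–3 succeed at the interim and the renal test was not significant at 2%, the renal composite is tested once more, as its last look, on all data to a cut-off date fixed before interim results are released. The blind is kept to database lock.

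Choose one alpha rule in advance:
- (a) the O'Brien-Fleming spending level for the actual renal events against 190, which holds one-sided error at 2.5% even if the stopping decision sees renal data; or
- (b) 4.4% two-sided, only if the plan also states that the decision to stop must not use the renal result.

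If the primary SAP already contains such a rule, a cross-reference in 9.7 is enough.

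The cost is a short addition to the text and one further Cox model, with no extra subjects, visits or follow-up. The downside is that a renal claim would rest partly on close-out data, so the cut-off and the blind need protection.
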